Even when DCIS patients opt to receive a less intensive treatment such as BCS without radiation therapy, they and their providers need to decide whether to undergo sentinel lymph node biopsy (SLNB). The role of SLNB for DCIS management is controversial in general and needs further scrutiny in particular if patients received BCS without radiation therapy. Significant debates continue about whether SLNB should be performed,⁶⁻⁸ with some experts advocating for its use.^{9,10} Proponents of SLNB cite concerns that occult microinvasive disease within the DCIS may not be detected histologically, with an estimated prevalence of 1.4% to 12%.¹¹ However, among DCIS patients who receive radiation therapy the likelihood of local recurrence with axillary involvement is low,¹² and routine SLNB is not recommended.¹³ Of note, radiation therapy has also been shown to control micrometastasis if present.¹⁴ On the other hand, if we plan to empower DCIS patients to choose less intensive management options, such as BCS without radiation therapy, understanding the role of SLNB will be crucial.

A systematic literature review has shown that evidence gaps exist regarding the benefits of SLNB for DCIS.¹⁵ As far as we know, no study has yet examined SLNB among DCIS patients who received BCS. Because of the current call for less intensive treatment, it is imperative to understand the benefits or harms for DCIS patients who received BCS. A large randomized controlled trial would be providing the best evidence to guide treatment recommendations, but the results would not be available for at least 10 years. Our project will use existing data to swiftly provide comprehensive information about comparative effectiveness across the DCIS care continuum in an observational study setting.

Study objectives

Using the Surveillance, Epidemiology, and End Results (SEER)-Medicare linked data, our project's overarching aims are:

Among older women with DCIS who have received BCS as their first surgery, to compare the outcomes of receiving SLNB vs. not receiving SLNB within 6 months of DCIS diagnosis:

Aim 1: We will determine associations between SLNB and acute/subacute side effects, including lymphedema, pain, and limitation of movement of upper extremity from the first BCS to 9 months post-diagnosis.

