Aim 2: We will determine associations between SLNB and long-term outcomes, including breast cancer specific mortality, ipsilateral invasive breast cancer diagnosis, subsequent mastectomy as treated recurrence, and lasting side effects, from >9 months post-diagnosis to death or the end of this study period.

Study design

We will conduct a retrospective cohort study. Using the most up-to-date SEER-Medicare database, we will examine the impact of SLNB on clinical outcomes of women with newly diagnosed DCIS among the Medicare population. The nature of SEER-Medicare linking Medicare claims records to tumor registries participating in the NCI's SEER program allows us to select study population based on precise demographic and clinical characteristics of the patients. In our study, the population is DCIS patients older than 67 years (hereafter referred to as older women) who were enrolled in a fee-for-service Medicare program and resided in the SEER areas from 1998 to 2011 (1998-2013 for Aim 2) and who were followed up to 2012 (2015 for Aim 2).

Methodology

Our study population are generated within the SEER-Medicare linked database. To identify patients with DCIS, we will use histology and behavior codes, which are converted from the ICD-O-3 codes that tumor registries are required to report to SEER for all cases.¹⁶ Specifically, we will identify breast “cancer” patients with in situ tumor behavior (behavior code = 2). DCIS patients will be further limited to those with ICD-O-3 codes consistent with epithelial origin. We select age 67 as a cut-off value because we plan to use two years of claims data to identify patient comorbidities and to control for them in our statistical models, and data is first available at age 65.

Our Aim 1 cohort will include DCIS patients who received BCS as their first surgery (i.e. excluding patients who received mastectomy first). We expect that patients who received BCS with SLNB (compared with those who received BCS without SLNB) would be more likely to end up with mastectomy, and thus would be more likely to have side effects. Findings of the associations between SLNB and mastectomy as the final treatment for DCIS would be informative. We intend to include these patients in Aim 1 so that we can provide a comprehensive picture regarding side effects of SLNB in the context of less intensive managements.

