Our Aim 2 will examine the long-term outcomes between patients who received BCS without SLNB and patients who received BCS with SLNB. Patients who received BCS in the beginning yet ended up with mastectomy for their primary DCIS will be excluded. For patients who received BCS plus RT, SLNB will not likely provide any benefits since RT is able to control small lesions. However, we plan to determine the effects of SLNB among patients who received BCS without RT, which will have important clinical implications.

The time period for defining the cohort for the Aim 1 will be between January 1998 and December 2011. Using medical claims for this cohort, we will identify any side effects within a

9-month window (from DCIS diagnosis to 9 months post-diagnosis). The time period for defining the cohort for the Aim 2 will be from January 1998 to December 2012, and patients will be followed from 9 months after DCIS diagnosis through the latest date to which data is available in SEER-Medicare. For instance, the next SEER-Medicare linked dataset will have overall mortality through December 2015, breast cancer specific mortality through December 2013, and claims data (to identify treated recurrence) through December 2014.

We identify interventions and comparators in our study using specific international classification of Diseases, Ninth Revision, (ICD-9) codes, CPT codes and HCPCS codes. We will limit our sample to DCIS patients who received BCS as their first surgery; that is, we exclude patients whose first surgery is mastectomy, because we are only interested in patients who receive less intensive treatment and their outcomes. Because SLNB is performed by a surgeon, we identify it within a window consistent with those used in prior literature to identify breast cancer surgery, that is, between the date of the first BCS and 6 months after DCIS diagnosis. We are aware that patients may receive BCS first and mastectomy later for their primary DCIS. Furthermore, we realize that SLNB may affect whether or not patients receive mastectomy.

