Based on the input of our patient and professional advisory committee members, we propose the following outcomes of interest in this project. In Aim 1 we focus on acute/sub-acute side effects. Secondary outcomes include treatment received. In Aim 2, our primary outcomes include breast cancer specific mortality, incident ipsilateral invasive breast cancer occurrence (based on ipsilateral invasive breast cancer from SEER) and treated recurrence (based on follow-up mastectomy). Secondary outcomes include overall survival and lasting side effects. Overall survival, expected to be similar, would be used as a benchmark outcome to check performance of our model.

In addition to the key exposures (interventions and comparators) and endpoints (outcomes of interest), we will further select covariates, including patient demographics, comorbidities, tumor characteristics and prior healthcare utilization, based on prior literature and our experience. We plan to include the following covariates to control for confounding. For patient demographics, we will include patient's age, sex, ethnicity, marital status and years of diagnosis. For geographical and social-economical characteristics, we will include income, education and metropolitan residence. For patient's comorbidities, we plan to include Elixhauser comorbidity index, disability index and prior hospitalization. For DCIS characters, we will include grade, size, comedonecrosis and hormone receptor status. For health care system utilization, we will consider prior influenza vaccination, physician visit, MRI use and surgeon's volume. Last, to control for other treatment patients have received, we will adjust for mastectomy and radiation therapy.

Data management and statistical analysis

We plan to create a dataset for this project. Each patient in the SEER-Medicare dataset has a unique patient identification number. Using this information, we will be able to collect patient demographics and DCIS characteristics from the SEER registry as well as claims data from Medicare on what treatment patients have received or what side effects they have experienced. We will manage the dataset in a suitable manner that fully complies with the SEER-Medicare data use rules and confidentiality.

As a secondary data analysis, we will be unable to prevent missing data from the original dataset. We do, however, set a priori exclusion and inclusion criteria for the creation of our cohort. We

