For multivariable analyses, we will use conditional logistic regression models for acute/subacute side effects (primary outcomes) and treatment received (mastectomy or radiation therapy; secondary outcomes) in Aim 1, with conditioning on the matched variable. For primary outcomes, we will run 2 models, with or without controlling for treatment received. We will report adjusted odds ratios of SLNB on these outcomes. In Aim 2, we will apply time-to-event models to test whether the intervention is associated with better outcomes, including primary and secondary outcomes. We will report adjusted hazard ratios of SLNB on these outcomes. The proportional hazards assumption will be evaluated for each model using a variety of methods (evaluation of Kaplan-Meier and log(-log) survival plots, Schoenfield residuals, and covariate x time interactions). If the proportional hazards assumption is violated, we will instead use parametric survival models, using AIC and BIC to determine the best parameterization (exponential, Weibull, generalized gamma, Gompertz, lognormal, or loglog). All time-to-event models will incorporate a shared frailty term for the matching group, and will include covariates that are not balanced by matching. These models will allow us to test for association between various factors (grade, tumor size, and estrogen receptor status) and outcomes.

In order to identify suitable patient subgroups that may be able to forego SLNB, we plan to explore the following stratification schemes in Aim 2 analysis: 1. Stratify patients by receipt of radiation therapy; 2. Stratify patients by key DCIS characteristics, including grade, comedonecrosis and tumor size; 3. Stratify patients by their predicted life expectancy, given their age, sex and comorbidities.

Expected outcomes of the study

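### Aim 2 compares mortality only in women who did not convert to mastectomy, an event the plan links to SLNB, and no sensitivity analysis keeps all BCS-first women

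*Combined protocol and SAP*

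**What the plan says.** Study objectives sets one target population for both aims: "Among older women with DCIS who have received BCS as their first surgery, to compare the outcomes of receiving SLNB vs. not receiving SLNB". The exposure window closes 6 months after diagnosis.

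The Methodology section narrows this for Aim 2: "Patients who received BCS in the beginning yet ended up with mastectomy for their primary DCIS will be excluded". It also links the exposure to the excluded event twice. In the Aim 1 cohort description, women with SLNB "would be more likely to end up with mastectomy, and thus would be more likely to have side effects". In the description of how SLNB is identified: "Furthermore, we realize that SLNB may affect whether or not patients receive mastectomy".

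The two aims treat these women differently. Aim 1 keeps them and makes mastectomy within 6 months a secondary outcome. For its side-effect outcomes the plan says: "For primary outcomes, we will run 2 models, with or without controlling for treatment received". Aim 2 has breast cancer specific mortality among its primary outcomes and overall survival as a secondary (benchmark) outcome, both followed from 9 months after diagnosis. Its analyses are stratified by radiation therapy, DCIS characteristics and predicted life expectancy, with this purpose: "In order to identify suitable patient subgroups that may be able to forego SLNB".

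**The concern.** A woman deciding about SLNB at or after her first BCS does not know whether she will later convert to mastectomy. The objective asks about her, but the Aim 2 mortality estimates apply only to women who turned out not to convert.

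Two things follow. First, if conversion is related to prognosis that the plan does not control, and the relation differs by SLNB status, the retained groups can differ in risk even when SLNB has no effect. Second, any effect of SLNB on mortality that acts through conversion is left out.

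The stake is a primary outcome in an analysis meant to inform who may go without SLNB. Readers would have no means of judging whether the mortality result depends on the restriction.

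**Working it through.** **Does anything in the plan already restore these women for mortality?**

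- Matching uses baseline variables. It may reduce the problem through grade, size, comedonecrosis and receptor status, but it does not bring back excluded women or reach disease that is not seen histologically.
- The 9-month start avoids counting immortal time. It does not undo selection that happened earlier.
- The only named sensitivity analysis concerns missing values.
- None of the three Aim 2 stratifications involves conversion.
- The covariate list says: "Last, to control for other treatment patients have received, we will adjust for mastectomy and radiation therapy". In the restricted cohort, mastectomy for the primary DCIS is constant, so this changes nothing there.
- The Aim 1 mastectomy model shows differential conversion for diagnoses from 1998 to 2011, but it gives no mortality result.

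**How large could the effect be?** The plan states no conversion rate, mortality rate or sample size, so there is no figure to reproduce. What follows is an illustration with no true SLNB effect.

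Inputs:
- p, prevalence of occult microinvasion: 1.4% to 12%, from the background section (5% added as a middle value). It was not measured in this cohort.
- b and c, conversion in women without and with occult disease: assumed.
- r0 = 0.01 and r1, risk of breast cancer death without and with occult disease: assumed.

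Risk among retained women = [(1−p)(1−b)r0 + p(1−c)r1] / [(1−p)(1−b) + p(1−c)]. The apparent ratio is this risk with SLNB divided by the risk without.

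Worked at p = 0.12, r1 = 0.10:
- SLNB, b = 0.20, c = 0.30: (0.704×0.01 + 0.084×0.10)/0.788 = 0.01959.
- No SLNB, 0.10/0.10: (0.792×0.01 + 0.108×0.10)/0.900 = 0.02080. Ratio 0.942.
- No SLNB, 0.10/0.30: (0.792×0.01 + 0.084×0.10)/0.876 = 0.01863. Ratio 1.052.

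| Conversion without SLNB (b/c) | p = 1.4% | p = 5% | p = 12% |
|---|---|---|---|
| 10%/10% | 0.986 | 0.963 | 0.942 |
| 10%/30% | 1.011 | 1.031 | 1.052 |

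The direction depends on the retained ratio (1−c)/(1−b). With SLNB it is 0.70/0.80 = 0.875. Without SLNB it is 1.00 in the first row and 0.70/0.90 = 0.778 in the second. If the two groups have equal retained ratios (for example 20%/20% against 10%/10%), the apparent ratio is 1.000, even though conversion is commoner with SLNB.

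**Grid.** p in {0.014, 0.05, 0.12}, r1 in {0.05, 0.10}, SLNB b in {0.10, 0.15, 0.20, 0.25}, SLNB c in {0.2, 0.3, 0.4, 0.5}: 96 cases per comparator. For the 10%/30% comparator, the 24 cases with c = 0.2 make SLNB lower conversion in occult disease, against the plan's own expectation, and are dropped.

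| Comparator | Cases | Min | Median | Max | Within 0.95–1.05 |
|---|---|---|---|---|---|
| 10%/10% | 96 | 0.785 | 0.967 | 1.030 | 59 |
| 10%/30% | 72 | 0.877 | 0.993 | 1.082 | 60 |

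In total 119 of 168 cases (71%) lie within 5% of 1. By prevalence the counts are 56 of 56 at 1.4%, 39 of 56 at 5%, and 24 of 56 at 12%. The three extremes (0.785, 0.877 and 1.082) all need 12% prevalence and tenfold mortality. No credit is given for matching on tumor characteristics.

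**Timing of SLNB.** SLNB counts as exposure up to 6 months after diagnosis, so it may fall at or after the mastectomy. This is harmless in the restricted cohort but matters once converters are kept. Suppose 20% have SLNB before any mastectomy, the rest convert at 10%/30%, and half of those converters have SLNB at mastectomy. At p = 0.12 and r1 = 0.10:
- Counted as exposed: 0.88×(0.20 + 0.80×0.10×0.5) = 0.2112 ordinary and 0.12×(0.20 + 0.80×0.30×0.5) = 0.0384 occult. Risk 0.005952/0.2496 = 0.02385.
- Counted as unexposed: 0.88×0.80×0.95 = 0.6688 and 0.12×0.80×0.85 = 0.0816. Risk 0.014848/0.7504 = 0.01979.
- Null ratio 1.205 (1.132 at 5%, 1.049 at 1.4%).

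Counting only SLNB done before, or without, a completion mastectomy returns the ratio to 1.00. These inputs are also assumed.

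**The case against.** The restriction is disclosed and is a choice of question. Aim 2 is described as BCS with against BCS without SLNB, with emphasis on women who did not have radiation therapy. For treated recurrence, measured by follow-up mastectomy, women who have already had the mastectomy are largely not at risk, so excluding them is reasonable. Much the same can be said for ipsilateral invasive cancer. Leaving out an effect that acts through conversion is a difference in estimand, not an error. All of this stands, and it is why the restricted cohort should stay.

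The plan also does not ignore conversion. Aim 1 models mastectomy by SLNB status, and outcome frequencies are to be tabulated by group, so readers will see differential conversion for most of the Aim 2 diagnosis years. This stands too. What remains missing is an Aim 2 count and any mortality result in all BCS-first women.

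Finally, bias needs a particular pattern of conversion and may be negligible. A reader might infer that the exclusion makes SLNB look better than it is. The documents do not support that: they give no conversion rates by prognosis, and two plausible comparators give opposite directions. The grid's lean below 1 reflects the chosen inputs. Nor can every excluded mastectomy be called a consequence of SLNB, because some SLNB may be done at or after it.

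**Conclusion.** The point holds as a gap in the Aim 2 mortality analysis, not as a demonstrated bias. The text alone establishes that the mortality estimates apply to a narrower group than the objective names, that the plan links the narrowing event to SLNB, and that no planned analysis tests dependence on it.

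The size rests on assumption throughout, apart from the 1.4% to 12% prevalence range. Null ratios are 0.94 to 1.05 in the lead cases, 0.79 to 1.03 over the grid with the 10%/10% comparator, and 0.88 to 1.08 with the 10%/30% comparator. Most cases are within 5% of 1, and larger departures come mainly at the top of the prevalence range. It would go too far to say that the restricted estimates are invalid or that the restriction should be dropped. The addition is worth making because the plan itself acknowledges the risk and the check uses the same linked data. Confidence is medium.

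**What to change.** Keep the restricted Aim 2 cohort and add:

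1. A statement that its estimates apply to women whose final surgery for the primary DCIS was BCS.
2. The number excluded for mastectomy in each SLNB group, over the Aim 2 diagnosis years.
3. One pre-specified, unstratified sensitivity analysis of breast cancer specific mortality and overall survival in all BCS-first women, with the Aim 2 years and 9-month start. Re-match by the plan's own 2:1 Mahalanobis method. Do not adjust for completion mastectomy, despite its place in the covariate list, since that would condition on the same event again.
4. In that analysis, count as exposed only SLNB done before, or without, a completion mastectomy, and also report the result under the plan's own exposure window.

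Do not extend this analysis to lasting side effects under the revised exposure rule: harm from SLNB done at mastectomy would be assigned to the unexposed group.

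The cost is some protocol wording, a second matched cohort with balance checks, and a comparison of SLNB and mastectomy claim dates. The Aim 1 extract alone is not enough, because the Aim 2 years and follow-up are needed. The added estimate is less specific to women who kept BCS, so it should sit beside the restricted one and not replace it.

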will include only DCIS patients who have available claims data (i.e. are enrolled in fee-for-service coverage) during the period between cancer diagnosis and the end of the follow-up (Aim 1: 9 months after DCIS diagnosis; Aim 2: either death or the last date of claims released by SEER-Medicare). Statistically, we plan to create an “unknown” category to capture those patients who had a missing value. Additionally, we will conduct sensitivity analyses regarding whether or not excluding these patients would change our findings.

To compare baseline characteristics between intervention and control groups, we will conduct standard descriptive statistics using χ^2 tests for categorical variables and t-tests for continuous variables. We will tabulate the frequencies of outcomes of interests by the intervention vs. control group. We will use multivariable analyses to test our hypotheses while controlling for unbalanced covariates, as described below.

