We plan to control for selection bias using propensity score matching methodology.¹⁷ Specifically, the propensity score matching will be based on the Mahalanobis distance¹⁸ calculated using age, race, residence in a metropolitan county, comorbidity, prior influenza vaccination or prior visit to a primary care physician (both as proxies for access to care), income, preoperative MRI use, and tumor characteristics. Tumor characteristics include size, grade, comedonecrosis, and estrogen receptor status. By incorporating these factors in matching, we expect to substantially decrease bias and balance the risk for outcomes of interest between the SLNB and non-SLNB groups. We will use 2: 1 matching, as prior literature indicated that this approach results in improved precision without a commensurate increase in bias.¹⁹ To ensure robust and comprehensive matching, matches will be assigned by choosing the two best non-SLNB patient matches for each SLNB patient; when two or more SLNB patients match the same control (that is, have Mahalanobis distances minimized by the same control), one will be randomly selected as a match, and this process reiterates until all SLNB patients have two matched controls. We will assess the validity of the matching by comparing risk factors between the SLNB and non-SLNB groups using χ^2 tests. The difference in outcomes between the control and intervention groups will be estimated in a Kaplan-Meier curve. We will estimate the relative risk in the propensity score matched sample using the standard method for matched-pair data.²⁰ We will use the Cox proportional hazards models to investigate the association between various factors (grade, tumor size, and estrogen receptor status) and outcomes.²¹

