According to our specific aims, we propose different outcomes of interest. For Aim 1, our primary outcome is the side effect occurrence within 9 months post-DCIS-diagnosis. The side effects include lymphedema, pain and limitation of movement of extremities. Our secondary outcome for Aim 1 is treatment received. We will examine the relationship between SLNB and subsequent treatment received, including mastectomy within 6 months after DCIS diagnosis and radiation therapy within 9 months after DCIS diagnosis. For Aim 2, we propose several primary outcomes. We will measure the breast cancer specific survival with the timeframe from 9 months post-diagnosis to death or end of study period. We will also assess the ipsilateral invasive breast cancer occurrence and treated recurrence, including mastectomy, within the same timeframe. For Aim 2, our secondary outcomes include overall survival (a benchmark outcome to check the performance of analytic models) and lasting side effects.

As for detailed outcome measurements, we expect to have these estimates by the end of the project: 1. the difference in baseline characteristics between the intervention and control groups and χ^2 statistics that suggests difference significance; 2. the propensity score matching results, including matched cohort and the standardized difference that indicates the balance of matching; 3. the estimate in the main analysis, for example odds ratio, rate ratio or hazard ratio, that could represent the association of intervention and outcome; 4. the estimate in the stratified analysis that could describe the association of intervention and outcome in each clinical subgroup.

Duration of the project

We are anticipating the project to be completed within 18 months of time.

Ethical concerns

As a result of the nature of our observational design, we do not anticipate any ethical concerns as we are analyzing existing data. We expect this project will be exempt from full review. However, we will make sure that no member in the project would violate the rules and confidentiality required when analyzing SEER-Medicare database.

References

2. American Cancer Society. Cancer Facts & Figure 2013. Atlanta: American Cancer Soc; 2013

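### The Aim 1 side-effect window has two different start dates and an end date tied to diagnosis, so claims made before surgery may count as events and time at risk after sentinel node biopsy varies between women.

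*Combined protocol and SAP*

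**What the plan says.** The combined protocol and SAP defines the Aim 1 primary outcome in three places.

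- Study objectives, Aim 1: lymphedema, pain and "limitation of movement of upper extremity from the first BCS to 9 months post-diagnosis".
- Methodology: any side effects in a "9-month window (from DCIS diagnosis to 9 months post-diagnosis".
- Expected outcomes of the study: "our primary outcome is the side effect occurrence within 9 months post-DCIS-diagnosis". This gives an end point but no start.

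The Methodology identifies SLNB "between the date of the first BCS and 6 months after DCIS diagnosis". The Data management and statistical analysis section sets the end of the required fee-for-service coverage at "Aim 1: 9 months after DCIS diagnosis". It also names the model: "we will use conditional logistic regression models for acute/subacute side effects (primary outcomes". Matching uses "age, race, residence in a metropolitan county, comorbidity, prior influenza vaccination or prior visit to a primary care physician", together with income, preoperative MRI and tumor characteristics. For the primary outcomes "we will run 2 models, with or without controlling for treatment received". Time from diagnosis to surgery is neither a matching variable nor in the covariate list in the Methodology. No rule is given for side-effect claims dated before surgery.

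**The concern.** Side effects are the Aim 1 primary outcome and the harm side of the SLNB question. Two programmers working from this text could build two different primary endpoints, and nothing in the plan settles which applies.

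Two separate problems follow.

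- **Start date.** If counting begins at diagnosis, a pain or arm claim made before any operation is a primary event, although SLNB cannot have caused it. Such claims add similar background to both arms and hide part of any real difference.
- **End date.** Because the window closes at a fixed time after diagnosis, a woman operated on later is observed for less time after her operation. A yes/no outcome in a logistic model treats 3 months of observation like 9. If the arms differ in how soon surgery takes place, that alone moves the odds ratio.

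**Working it through.** The plan states no sample size, power, event rate or odds ratio for Aim 1, so there is no figure to reproduce. The inputs from the document are the 9-month end, the 6-month limit for SLNB and the two start dates. Everything marked as assumed is illustration.

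**1. Time after SLNB (document limits only).** Let s be the month of SLNB after diagnosis. Time after SLNB is 9 − s, and the pre-SLNB share of a window that starts at diagnosis is s/9.

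- s = 1: 8 months; 11%
- s = 2: 7 months; 22%
- s = 3: 6 months; 33%
- s = 6: 3 months; 67%

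Time after SLNB thus runs from 3 to almost 9 months. The range of 9 − s is the same under either start date.

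**2. Dilution (diagnosis start only).** Assume constant rates, a true doubling after SLNB, surgery at month s in both arms, and pre-surgical claims at c times the control post-surgical rate. The expected event ratio is [cs + 2(9 − s)] / [cs + (9 − s)].

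- s = 2, c = 1: (2 + 14)/(2 + 7) = 16/9 = 1.78
- s = 2, c = 0.5: (1 + 14)/(1 + 7) = 15/8 = 1.88
- s = 1: 17/9 = 1.89 with c = 1; 16.5/8.5 = 1.94 with c = 0.5
- s = 6, the latest permitted month: 12/9 = 1.33 with c = 1; 9/6 = 1.50 with c = 0.5

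The undiluted ratio is 2.0.

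The plan reports odds ratios, so the same case was put on that scale, with risk = 1 − exp(−cumulative hazard), a hazard ratio of 2 and surgery at month 2. With an assumed 9-month control risk of 5%, the odds ratio is 2.04 counting from BCS. Counting from diagnosis it is 1.91 (c = 0.5) or 1.81 (c = 1). With an assumed risk of 20%, it is 2.19 against 2.05 or 1.95.

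**3. Unequal time (BCS start, no true effect).** Let h = −ln(1 − r)/9, where r is the assumed 9-month risk. The risk for surgery at month s is then 1 − exp[−h(9 − s)]. With r = 10%, h = 0.0117. Surgery at month 1 gives odds exp(8h) − 1 = 0.0982, and surgery at month 2 gives exp(7h) − 1 = 0.0854. The odds ratio is 0.0982/0.0854 = 1.15 if the SLNB arm is operated on a month earlier, and 0.87 if a month later.

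Across r = 5% to 20%:

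- a one-month difference gives 1.15 to 1.16, or 0.86 to 0.87
- a two-month difference (months 1 and 3) gives 1.34 to 1.37, or 0.73 to 0.75
- with no difference between arms, the null odds ratio stays at 1

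**The case against.** The best defence is that the effect may be small. If most women have surgery soon after diagnosis, few pre-surgical claims can accrue. If timing is similar in the two arms, unequal time does not bias a null comparison. The document gives no timing data to contradict this, so the objection stands as to size. It does not remove the conflict between the two start dates, or the absence of any allowance for timing.

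Three stronger readings are tempting, but the document does not support them.

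- **That SLNB harm is understated.** Dilution toward 1 arises from claims before any surgery only if the Methodology wording governs. Unequal time can push the odds ratio either way.
- **That the Expected outcomes section also starts at diagnosis.** It gives only an end point and is compatible with a start at first BCS.
- **That a woman with BCS and SLNB together in month 7 would be a control.** The Study objectives define the comparison by SLNB within 6 months, and no latest date for BCS is stated, so the inference is plausible. However, the Methodology describes the 6-month limit as one used for breast cancer surgery generally, which may bound BCS too. The text does not settle her status.

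A short fixed window as the main analysis is also open to objection. Aim 2 begins after month 9, so events between the end of a 3-month window and month 9 would be in neither aim's main analysis. Such a window could also miss effects of later mastectomy, which the Methodology deliberately keeps in Aim 1. A 6-month window after surgery later than month 3 passes month 9 and exceeds the coverage requirement. These points stand, and the fix respects them.

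The Kaplan-Meier curve planned for outcomes has no stated time origin and does not change the Aim 1 primary model.

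**Conclusion.** The concern holds in this form. The start date of the Aim 1 primary outcome is contradictory: first BCS in the Study objectives, diagnosis in the Methodology. Under the Methodology wording, pre-surgical claims count as events and would tend to pull the odds ratio toward 1. Under every wording, observation after SLNB ranges from 3 to almost 9 months, and the planned matching and model ignore it, so a timing difference between arms could bias the result in either direction.

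The conflict and the 3-to-9-month range come straight from the text. The size of any bias is unknown. The values 1.78 and 1.88 against 2.0 apply only to the diagnosis start. They assume a true doubling, constant rates, surgery at month 2 in both arms, and a pre-surgical claim rate equal to or half the control post-surgical rate. The month-6 values show the permitted extreme, with nothing to suggest that it is common. The plan should be corrected because the outcome is primary and the repair uses existing data.

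**What to change.** 1. State one start date, first BCS, in the Study objectives, Methodology and Expected outcomes sections, and do not count side-effect claims dated before it.
2. State that first BCS must fall within 6 months of diagnosis, so that no woman whose surgery comes after the exposure window is classed as a control.
3. Keep the end at 9 months after diagnosis, so that Aims 1 and 2 remain contiguous.
4. Report time from diagnosis to first BCS by arm, and match on it or adjust for it in the Aim 1 conditional logistic model.
5. As a sensitivity analysis, use a window of equal length after surgery for all women. Extend the coverage requirement in the Data management and statistical analysis section where that window passes month 9.

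One limit remains. When SLNB follows first BCS at a later date, claims between the two still count against SLNB, and the report should say so.

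The cost is a change of wording and modest extra programming. A few women with late first BCS are dropped, and somewhat fewer events are counted than with a diagnosis start.
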